1. MODIFICATION HISTORY

Version Author Changes from previous version						
1.0	[name]	N/A - First version.				
1.1	[name]	Corrected after the March, 28th 2024 meeting with investigators				

2. LIST OF ABBREVIATIONS

AE: Adverse Event

ANCOVA: Covariance analysis

ATC1: Anatomical main group

ATC2: Therapeutic subgroup

CHE: Chronic Hand Eczema

CI: Confidence Interval

DLQI: Dermatology Life Quality Index

EASI: Eczema Area and Severity Index

eCRF: electronic Case Report Form

EQ-5D-5L: 5-Levels EQ-5D

HIV: Human Immunodeficiency Virus

IGA: Investigator's Global Assessment

IgE: Immunoglobulin E

ITT: Intention-To-Treat

MCID: Minimal Clinically Important Difference

MedDRA: Medical Dictionary for Regulatory Activities

mTLSS: modified Total Lesion Symptom Score

OLS: Ordinary Least Squares

PaGa: Patient's Global assessment

PP: Per-Protocol

PT: Preferred Term

Q1: 25th percentile

Q3: 75th percentile

SAP: Statistical Analysis Plan

SD: Standard Deviation

SOC: System Organ Class

VAS: Visual Analog Scale

WHODD: World Health Organization Drug Dictionary

3. INTRODUCTION

This Statistical Analysis Plan (SAP) provides a comprehensive and detailed description of the statistical strategy and methods to be used to perform the final analysis of the data for the DUPECZEMAIN study planned to be conducted after the end of the study.

This SAP is based on the protocol version 6.0 dated June 26th, 2023 and on the Clinfile eCRF printed February 02nd, 2024. It was validated before database lock of the study and before the unblinding of the database. Treatment allocation will be provided at the end of the study for all subjects after last subject has completed the study, complete cleaning of database and statistical analysis plan validated.

Further analyses might be conducted based on Health Authority requests or as deemed necessary.

4. STUDY OBJECTIVES

The primary objective of the study is to demonstrate that dupilumab is more effective than placebo for the treatment of patients with moderate to severe chronic hand eczema (CHE) who are resistant or intolerant to highly potent topical corticosteroids as determined by the evolution at week 16 of the modified total lesion symptom score (mTLSS) since baseline.

Secondary objectives are:

- To demonstrate that dupilumab is more effective than placebo to improve pruritus induced by CHE at week 16 as compared to baseline.
- To demonstrate that dupilumab is more effective than placebo to improve pain induced by CHE at week 16 as compared to baseline.
- To demonstrate that dupilumab is more effective than placebo to improve quality of life at week 16 as compared to baseline.
- To demonstrate that dupilumab is more effective than placebo to improve sleep loss induced by CHE at week 16 as compared to baseline.
- To demonstrate that dupilumab is more effective than placebo to induce clearance or almost clearance of CHE at week 16 as defined by the investigator and by the patient.
- To demonstrate that dupilumab is more effective than placebo to improve work productivity at week 16 as compared to baseline.
- To evaluate the efficacy of dupilumab on other parts of the body compared with placebo, in patients with eczema not limited to the hand.
- To evaluate the evolution of laboratory parameters of patients receiving dupilumab compared to those receiving placebo.
- To evaluate the safety of dupilumab as compared to placebo throughout the course of the study.

5. INVESTIGATIONAL PLAN

5.1. OVERALL STUDY DESIGN AND PLAN

The DUPECZEMAIN study is a multicenter (conducted in 4 centers in France), randomized, double-blind, 2-arm parallel-design study comparing dupilumab to a placebo in patients with moderate to severe CHE who are resistant or intolerant to highly potent topical corticosteroids.

The study consists in three phases: screening, treatment phase (16 weeks) and follow-up post treatment (4 weeks).

A patient is eligible for the study (and to start the study treatment) only if complying with all the inclusion/non-inclusion criteria, that is, fulfilling all inclusion criteria without matching any non-inclusion criterion. Inclusion and non-inclusion criteria are checked at the Screening visit, which takes place 1 to 4 weeks before the start of study treatment.

The inclusion criteria are as follows:

- Adult Patients (≥18 years) affiliated to a social insurance protection regimen.
- Patients with moderate to severe chronic (>6 months) hand eczema with an Investigator global assessment (IGA) of 3 or 4 (out of a scale of 0 to 4).
- Patients intolerant (according to the physician) or resistant to highly potent topical corticosteroids.
 Inadequate response (resistance) to highly potent topical corticosteroids is defined as a history of failure to achieve and maintain remission or a low disease activity state (comparable to an IGA score of 0 [indicating clear] to 2 [indicating mild]) despite treatment with a daily regimen of highly potent topical corticosteroids applied for 14 days or for the maximum duration recommended for highly potent topical corticosteroids.
- Patients who are able to understand the study procedures including the ability to complete patient-oriented questionnaires.
- Patients who are able to apply a stable dose of emollients within 7 days before the baseline visit.
- Patients who agree to sign the written informed consent.

The exclusion criteria are as follows:

- Hypersensitivity to dupilumab or to any of its ingredients.
- Patients under adult autonomy protection system.
- Any other condition (e.g., psoriasis) on the hands that according to the investigator will impair the ability to evaluate treatment effect.
- Treatment with topical corticosteroids or topical calcineurin inhibitors within one week of baseline.
- Treatment with oral immunosuppressants (including cyclosporine, methotrexate, azathioprine, mycophenolate mofetil), alitretinoin or phototherapy within 4 weeks of baseline visit.
- Treatment with an investigational drug within 8 weeks (or 5 half-lives) of baseline.
- Active chronic infection requiring the use of a systemic antibiotic within 2 weeks before study start.
- Known or suspected history of immunosuppression, including history of invasive opportunistic infections (e.g., tuberculosis, histoplasmosis, listeriosis, coccidioidomycosis, pneumocystis, aspergillosis) despite infection resolution; or unusually frequent, recurrent, or prolonged infections, per investigator judgment.
- History of human immunodeficiency virus (HIV) infection or positive HIV serology at screening.
- Positive for hepatitis B surface antigen, hepatitis B core antibody, or hepatitis C antibody at the screening visit.
- Patients with known helminth infections.
- Pregnant or breastfeeding women, or women planning to become pregnant or breastfeed during the study.
 Women of childbearing potential who are sexually active and unwilling to use an adequate birth control method.

After confirmation of eligibility, patients are randomly allocated by a computer-generated randomization system in a 1:1 ratio to receive one of the following two treatment strategies:

- Dupilumab 300 mg for subcutaneous administration. Two initial injections of 300 mg dupilumab will be administered, followed by one injection of 300 mg every 2 weeks until week 14.
- Placebo with the same administration procedure.

The randomization is performed in a stratified manner based on the presence or not of a personal history of atopic dermatitis, as it is expected to be the major factor potentially influencing the primary endpoint. Baseline severity is not expected to influence the primary endpoint, as the relative change in mTLSS is not anticipated to be influenced by disease severity.

After randomization, study treatment is begun as soon as possible.

Some treatments/procedures are prohibited during the study as either they may influence disease outcome or may pose a safety risk for patients. Treatment with the following concomitant medications is prohibited during the study

- Treatment with immunomodulating biologics.
- Treatment with an investigational drug (other than dupilumab).
- Treatment with topical corticosteroids or topical calcineurin inhibitors; such agents should not be administered during the study.
- Treatment with systemic corticosteroids or non-steroidal systemic immunosuppressive drugs (e.g., cyclosporine, methotrexate, mycophenolate-mofetil, azathioprine, etc.), except if critically medically needed to treat concurrent medical conditions (e.g., asthma).

Study drug will be temporary discontinued (5 half-life before and after vaccination) if a treatment with live (attenuated) vaccine is used through week 16.

In addition, major surgery procedure and phototherapy (medical device or tanning) are prohibited during the 16-week treatment period.

Rescue therapy: if a patient presents with a severe flare of CHE during the course of the study which cannot be managed with emollients and requires intervention, a unique rescue 2-week course of highly potent corticosteroid (betamethasone dipropionate cream) will be administered. The amount of drug used will be recorded. Study treatment will be unchanged.

In contrast, emollients are approved for use in patients during the course of the study. Patients are allowed to take anti-histamines if medically indicated during the study. Patients with comorbid asthma should be on stable treatment. Any change in the dosage of anti-histamines should be captured in the source documents and electronic Case Report Form (eCRF).

The end of the study does correspond to the end of study participation. Patient premature withdrawal from treatment period is mandatory in the following situations: Investigator judgment, Pregnancy or suspected pregnancy, Unacceptable adverse event(s)/serious adverse event(s), Participant decision (wants to discontinue the treatment and agrees to undergo follow-up assessments), Participant withdrawal of consent, Death.

5.2. STUDY ENDPOINTS

5.2.1. Primary endpoint

The primary endpoint measure is percentage change of the severity score mTLSS from baseline to week 16. The mTLSS combines an evaluation of hand eczema lesions severity including 6 key signs (erythema, desquamation, lichenification/hyperkeratosis, vesiculae, oedema, fissures) and the intensity of pruritus and pain.

5.2.2. Secondary endpoints

Secondary endpoints include the following:

• Evolution of pruritus associated with CHE at week 16 since baseline measured with a visual analog scale (VAS).

- Evolution of pain associated with CHE at week 16 since baseline measured with a visual analog scale.
- Improvement of quality of life at week 16 since baseline measured by Dermatology Life Quality Index (DLQI) (1) and 5-levels EQ-5D (EQ-5D-5L)(2).
- Evolution of sleep loss associated with CHE at week 16 since baseline measured with a VAS.
- Clearance or almost clearance of hand eczema at week 16 as defined by an Investigator's global assessment (IGA)(3) of 0 or 1.
- Clearance or almost clearance of hand eczema at week 16 as assessed by the Patient's global assessment (PaGa)(4) of 0 or 1.
- Improvement of work productivity at week 16 since baseline as assessed by the questionnaire Work Productivity and Activity Impairment (WPAI)(5).
- Evolution of the Eczema Area and Severity Index (EASI) at week 16 since baseline in patients who have eczema on other parts of the body than the hands(6).
- The safety throughout the course of the study (at 20 weeks since baseline) by monitoring adverse events, serious adverse events, injection site reactions.
- Evolution of laboratory parameters (full blood count and total immunoglobulin E (IgE)) at week 16 since baseline.

5.3. DETERMINATION OF SAMPLE SIZE

The sample size is determined by the primary objective of the study, that is, to compare the percentage change in mTLSS score from baseline to Week 16.

His calculations are based on a clinically meaningful absolute difference between groups in the mean percentage change in mTLSS score from baseline to Week 16 of -25% (greater percentage decrease expected in dupilumab compared with placebo). Assuming a standard deviation of 40% in both groups, sample size of 84 patients (42 by group) will achieve over 80% power to detect such a difference with a significance level (type-I error) of 0.05 using a two-sided two-sample t-test (7).

To account for potential non-evaluable patients estimated to 10%, a total of 94 patients will have to be randomized.

6. GENERAL STATISTICAL CONSIDERATIONS

6.1. DESCRIPTIVE STATISTICS

Descriptive statistics for quantitative parameters will include the following: number of missing data, number of non-missing observations, mean, Standard Deviation (SD), 25th percentile (Q1), median, 75th percentile (Q3), minimum and maximum values.

Minimum and maximum values will be presented with the same decimal precision as collected. Mean, Q1, median, and Q3, will be displayed with one more decimal place than collected. SD will be displayed with one more decimal place than mean.

Descriptive statistics for qualitative parameters will include the following: number of missing data, number of non-missing observations, counts, and percentages.

Percentages will be calculated on non-missing data, unless otherwise specified (e.g. with imputation of a value according to described rules). Percentages will be displayed with one decimal place.

Of note, for each categorical parameter, all categories specified in the electronic eCRF will be displayed even if there is no observation; in the case there is no observation, result will be displayed as "-" to represent (0.0%)".

This data will be summarized in a table like the one below:

_	Placebo arm	Dupilumab arm	Total
	(N=)	(N=)	(N=)
Qualitative parameter			
n/missing	n/na	n/na	n/na
Modality 1	n (%)	n (%)	n (%)
Modality 2	n (%)	n (%)	n (%)
Quantitative parameter			
n/missing	n/na	n/na	n/na
Mean (SD)			
Médian			
p25; p75			
Min ; Max			

6.2. INFERENTIAL STATISTICS

The primary objective of study is to demonstrate that dupilumab is more effective than placebo for the treatment of patients with moderate to severe CHE who are resistant or intolerant to highly potent topical corticosteroids as determined by the evolution at week 16 of the mTLSS since baseline. The study is sized on the basis of the primary objective only. The study uses a single primary endpoint and has a confirmatory statistical strategy that pre-specifies just one single null hypothesis relating to the primary endpoint and no formal interim analysis.

The primary analysis of the primary endpoint, which forms the basis for the sample size justification, involves comparing the percentage change from baseline to week 16 of the severity score mTLSS between the experimental arm (dupilumab) and the control arm (Placebo) using a covariance analysis. This analysis includes the group, the stratification factor (personal history of atopy), the baseline mTLSS score and the interaction between the stratification factor and the treatment arm as covariables. The treatment effect is tested at a 5% significance level.

The null hypothesis H_0 is that the percentage change in experimental arm is the same as the percentage change in control arm. The alternative hypothesis H_a is that percentage change in experimental arm differs from percentage change in control arm.

All other analyses of the other efficacy endpoints, are intended to yield supportive evidence related to the primary objective and to provide additional characterization of treatment effects, and no claims are intended. Confidence Intervals (CIs) and statistical tests, if any, that are part of these analyses are of exploratory nature and will be performed without any adjustment of type I error. They will be two-sided and performed each at the 0.05 significance level, unless otherwise specified.

Similarly, analyses on safety endpoints are used in an exploratory manner. CIs and statistical tests, if any, will be two-sided and performed each without any adjustment for multiplicity at the 0.05 significance level.

6.3. GENERAL DATA HANDLING CONVENTIONS

6.3.1. Definition of reference date(s)

Two dates may be used as reference date according to the purpose of the analysis: the date of randomization and the date of first study treatment administration.

In all tables and listings, reference date(s) will be clearly identified.

6.3.2. Calculation of durations and conversion factors

Durations in days are computed as the difference between end and start dates of the assessment under consideration.

The following conversion factors are used to convert days into weeks or months or years, and vice versa:

- 1 week = 7 days.
- 1 month = 30.4375 days.
- 1 year = 365.25 days.

6.3.3. Definition of baseline value/result for safety parameters

Baseline value/result for safety parameters is defined as the last non-missing value/result of the parameter measured prior to the first study treatment administration.

6.3.4. Coding conventions

All medications are coded by Data Management according to World Health Organization Drug Dictionary (WHODD) format B3 version 2018.

All medical and surgical history, as well as all Adverse Events (AEs), are coded by Data Management according to Medical Dictionary for Regulatory Activities (MedDRA) version 21.0.

6.3.5. Handling of missing value for main judgement criteria

About the primary endpoint (percentage change in mTLSS score between visit 0 and visit 9), there are different possibilities depending on the analysis and the visit for which this data is missing:

• If the mTLSS score is completely missing or if more than 25% of items are missing during the first visit,

no imputation will be made and the participants will not be considered in any of the analyses (principal and sensitivity).

- If less than 25% of items are missing, this will be imputed by the value representing the patient's optimal state.
- If the mTLSS score is completely missing or if more than 25% of items are missing at all visits except the first, no imputation will be made and the participants will not be included in any of the analyses (principal and sensitivity).
- If the mTLSS score is completely missing or if more than 25% of items are missing at the visit 9 for less than 10% of randomized patients, no imputation will be performed.
- If the mTLSS score is completely missing or if more than 25% of items are missing at the visit 9 for more than 10% of randomized patients, but this score is entered for at least one visit between visit 2 and visit 8:
 - The last available data will be used for the primary efficacy analysis of the primary endpoint (the last available data per item if less than 25% of items are missing or the last available data for the full score if more than 25% of items are missing).
 - For the first sensitivity analysis, we will conduct multiple imputations, using chained equations (8) with a missing at random assumption, to address missing criteria.

 The imputation model will be carried out by arm in order to take into account possible interaction between the stratum and the arm (9). It will encompass both independent variables and the outcome, along with auxiliary variables predicting missingness and/or associated with the missing variables. Consequently, the imputation model will explicitly include the percentage change in mTLSS, baseline mTLSS and the randomization stratum. In addition to these variables, auxiliary variables will be added to the imputation model. These variables are the most likely to influence the judgement criterion and the possibility of missing data. Thus, the mTLSS scores at intermediate time (visit 3, visit 5 and visit 7) and raw IGA scores from baseline to V9 (scored from 0 to 4) will be added to the imputation model.
 - o For the second sensitivity analysis, no imputation will be made and the analysis will be based solely on available data.

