8.2. EXCLUSIONS FROM EFFICACY ANALYSES

8.2.1. Exclusions from the ITT population

There is no exclusion from the ITT population (primary set of patients for the efficacy analysis), all randomized patients being included in the ITT population.

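### SAP Section 6.3.5 lets the observed missingness choose the primary estimator (complete cases or last observation carried forward), with the switch set at the planned 10% non-evaluable rate

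*SAP*

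**What the plan says.** Section 6.3.5 sets the handling of the primary endpoint by the share of randomised patients without a usable mTLSS at visit 9 (score absent, or more than a quarter of its items absent).

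- Lower branch, score unusable "at the visit 9 for less than 10% of randomized patients, no imputation will be performed". The primary analysis is then a complete-case analysis.
- Upper branch, more than 10%, for patients with at least one score between visits 2 and 8: "The last available data will be used for the primary efficacy analysis of the primary endpoint". This is last observation carried forward (LOCF).
- Under the upper branch only, the section describes a first sensitivity analysis by chained-equations multiple imputation (MI), run by arm. It then describes a second, in which "no imputation will be made and the analysis will be based solely on available data".
- For patients with no usable score at any visit after the first, "no imputation will be made and the participants will not be included in any of the analyses (principal and sensitivity").

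Section 13.1.3 lists three sensitivity analyses without any condition: MI, available data and per-protocol. Section 7.1 places the primary analysis on the ITT population of all randomised patients, and Section 8.2.1 states "There is no exclusion from the ITT population". Section 5.3 inflates the sample size with the words "To account for potential non-evaluable patients estimated to 10" per cent. Section 6.3.6 repeats the 10% trigger for most secondary endpoints.

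**The concern.** The trial has one confirmatory test (Section 6.2), so its estimator should be known before the data are. Here it is known only once missing week-16 scores have been counted, and the cut lies at the rate the sample size anticipates. With 94 randomised, one patient decides the method.

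Neither branch is a safe default. LOCF treats an earlier score as the week-16 score, which distorts the difference when response is still developing. Complete cases can mislead when dropout depends on response and differs by arm. In the lower branch, as Section 6.3.5 is written, no analysis challenges the missing-data assumption: the available-data analysis is the primary analysis again, and the per-protocol set excludes patients not evaluable for the primary endpoint (Section 8.2.2).

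**Working it through.** **Inputs from Section 5.3.** Difference in "mean percentage change in mTLSS score from baseline to Week 16 of -25" per cent; SD 40 in both groups; 42 per group; "significance level (type-I error) of 0.05 using a two-sided two-sample t-test"; 10% non-evaluable; 94 randomised.

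**1. The plan's own figures.**
- Normal approximation: n per arm = 2 × (1.96 + 0.8416)² × (40/25)² = 40.2, so 41.
- Two-sample t-test at 42 per arm: non-centrality 25 / (40 × √(2/42)) = 2.86 on 82 degrees of freedom, power 80.8% (79.8% at 41).
- Inflation: 84 / (1 − 0.10) = 93.3, so 94.

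All reproduce. The sample size is not at fault.

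**2. Where the switch falls.** 9/94 = 9.6% gives complete cases and 10/94 = 10.6% gives LOCF. With X ~ Binomial(94, p), P(LOCF) = P(X ≥ 10):

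| Assumed true missing rate p | P(LOCF) |
|---|---|
| 5% | 0.019 |
| 8% | 0.219 |
| 10% (planned) | 0.468 |
| 12% | 0.704 |
| 15% | 0.913 |

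Exactly 10% cannot occur with 94 patients. With 90 randomised it would be 9 patients, with probability 0.139 at p = 10%, and no rule would apply.

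**3. Do the branches estimate the same thing?** The SAP gives no trajectories or dropout by arm, so all values here are assumptions. Take week-16 means of -60 (dupilumab) and -35 (placebo), true difference -25.

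*Dropout unrelated to outcome.* Complete cases then average -25. LOCF can be worked by hand:
- 10% missing in each arm, half of the change reached at the last visit: (0.9 × -60 + 0.1 × -30) − (0.9 × -35 + 0.1 × -17.5) = -57 + 33.25 = -23.75.
- 5% dupilumab, 15% placebo, half of the change reached in both: (0.95 × -60 + 0.05 × -30) − (0.85 × -35 + 0.15 × -17.5) = -58.5 + 32.375 = -26.1.
- The same rates, with no change carried forward on placebo: -58.5 − (0.85 × -35) = -58.5 + 29.75 = -28.75.

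*Dropout likelier after a poor week-4 response.* Simulated with means at weeks 4/8/12/16 of -30/-45/-55/-60 against -20/-28/-32/-35, SD 40, correlation 0.6. Ranges cover separate simulations that differ in the details of the dropout model.

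| Dropout, dupilumab/placebo | LOCF | Complete cases |
|---|---|---|
| 10%/10% | -24.1 to -24.3 | -25.1 |
| 20%/10% | -21.7 to -22.3 | -27.0 to -27.1 |
| 10%/20% | -25.2 to -25.3 | -23.0 to -23.6 |

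The gap is about 1 point in the first row, about 5 in the second and about 2 in the third. LOCF is further from -25 in the first two rows and nearer in the third.

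**4. Sections side by side.** Section 13.1.3 promises MI and available-data analyses in all cases and refers to Section 6.3.5 for the MI. That section places both under the above-10% bullet and rules out imputation below it. Sections 7.1 and 8.2.1 describe an all-randomised population. Section 6.3.5 leaves patients with no post-baseline score out of the primary and sensitivity analyses, and the lower branch also leaves out everyone without a visit-9 score.

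**The case against.** Several points on the other side stand.

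- **The rule is not discretionary.** It is pre-specified, mechanical and pooled over arms, and Section 3 has the plan validated before unblinding. A reader might infer that an analyst could pick the favourable method; the text gives no such freedom.
- **The 0.47 needs an equivalence.** Non-evaluable in Section 5.3 need not mean a missing visit-9 mTLSS. At 5% or 8% missing, LOCF is unlikely.
- **A near coin toss does not go with a 5-point gap.** Dropout of 20%/10% pools to 15%, where LOCF is chosen with probability about 0.91, so the complete-case result would seldom be the primary one. At 10%/10% the gap is about 1 point. Nor is LOCF always the worse method, as 10%/20% shows.
- **A large power loss does not follow.** A reader might put a 21.7-point LOCF effect at 42 per arm and read off 69% power. LOCF keeps patients who have any post-baseline score, so about 47 per arm is the relevant number and gives 74%; the 21.7 itself comes from assumed trajectories.
- **ITT is not flatly contradicted.** Sections 7.1 and 8.2.1 define membership, and no one loses it. The mismatch is with the set analysed. Under a missing-at-random model, patients with only a baseline would change the estimate little.
- **It is too strong to say that no missing-data sensitivity analysis is planned below 10%.** Section 13.1.3 does promise one; the two sections disagree.

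None of this supplies a reason for the primary estimator to change at a count of missing scores.

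**Conclusion.** The point holds. Section 6.3.5 does not fix one primary estimator: it gives complete cases below 10% missing, LOCF above, and nothing at exactly 10%. At the planned rate the outcome is close to even (0.47 for LOCF), provided that non-evaluable means no usable week-16 score.

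The consequence is moderate and uncertain in direction: about 1 point on a 25-point design effect with equal 10% dropout, and about 2 to 5 points with unequal, response-related dropout. These sizes rest on assumed trajectories and dropout, not on SAP figures.

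Two inconsistencies need no simulation. Sections 6.3.5 and 13.1.3 disagree on which sensitivity analyses exist below 10%, and the analysed set is narrower than the all-randomised set of Sections 7.1 and 8.2.1.

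**What to change.** Before the allocation is released:

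1. Delete the 10% trigger from Section 6.3.5.
2. Make the by-arm chained-equations MI already described there the primary analysis for any amount of missing week-16 data. State the number of imputations. Include every randomised patient with a baseline score, also those with no later visit.
3. Keep complete cases and LOCF as sensitivity analyses, and add a delta-adjusted version of the MI with a stated range of deltas, since nothing in the plan now goes beyond missing at random.
4. Align Section 13.1.3 with this, and remove the same trigger from Section 6.3.6.

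The cost is mostly SAP wording, some extra programming and pooled reporting. One check is needed. The imputation model has 11 variables (percentage change, baseline mTLSS, stratum, three intermediate mTLSS scores, five IGA scores) for about 47 patients per arm, and visit-9 IGA will often be missing together with visit-9 mTLSS. Its stability should be confirmed on blinded data, with a reduced set of auxiliary variables named in advance. Another fixed method, such as a mixed model over visits 3, 5, 7 and 9, would also remove the switch; MI is the shorter route because the SAP already contains it. The sample size does not change.
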